## 1.0 Study Summary

Study Title	Open-label, single-blinded, observational, prospective, 36-month, longitudinal, controlled study to assess the efficacy of siponimod (Mayzent®) on microglia in patients with active secondary progressive forms of multiple sclerosis
Study Design	Open label, single-blinded, observation, prospective, longitudinal BNAC MRI analysts are blinded to subject's medication treatment.
Primary Objective	The assessment of the effect of Mayzent over at least 24 months on the evolution of microglia pathology in patients with active secondary-progressive (SP) MS.
Secondary Objective(s)	(a) compare the effect of Mayzent to the control group of active SPMS patients treated with ocrelizumab (Ocrevus®), as measured by changes in microglial activation in the lesional and non-lesional normal appearing (NA) WM and GM, and in the peri-plaque area of chronic lesions in the brain; (b) the relationship between changes in microglial activation in the lesional and non-lesional normal appearing

PROTOCOL TITLE: Open-label, single-blinded, observational, prospective, 36-month, longitudinal, controlled study to assess the efficacy of siponimod (Mayzent®) on microglia in patients with secondary progressive forms of multiple sclerosis

	
(NA) WM and GM, and in the peri-plaque area of chronic lesions in the brain and clinical and behavioral outcomes.
 
(b) to validate the quantification approach and to use as a statistical control group (15 HCs) when looking at an increase in TSPO in a parametric map of the brain

Research Intervention(s)/ Investigational Agent(s)	MRI and PET scans, clinical visits, questionnaires, eye exam, blood sampling.
IND/IDE #	
Study Population	
Individuals with active Secondary Progressive Multiple Sclerosis (SPMS)
 
Activity is determined by MRI activity (contrast-enhancing lesions; new and unequivocally enlarging T2 lesions) and/or clinical relapses in the 24 months prior to the study baseline.
 
15-age-matched healthy controls (10 females and 5 males aged between 18-65 years)

Sample Size	60 MS patients; 15 healthy controls
Study Duration for individual participants	
2-3 years: MS Patients
 
Approximately 4 hours: healthy controls – 1 timepoint

Study Specific Abbreviations/ Definitions	

AEs	Adverse Events
BBB	Blood-brain-barrier
BICAMS	Brief International Cognitive Assessment for MS
BNAC	Buffalo Neuroimaging Analysis Center

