## 2.0 Study Intervention/Investigational Agent

2.1 *If the research involves drugs or device, describe your plans to store, handle, and administer those drugs or devices so that they will be used only on subjects and be used only by authorized investigators.*

- *If the control of the drugs or devices used in this protocol will be accomplished by following an established, approved organizational SOP (e.g., Research Pharmacy SOP for the Control of Investigational Drugs, etc.), please reference that SOP in this section.*

Response: The treatment provided to subjects is part of their routine clinical care as determined by their neurologist and the patients themselves. This project will not administer any drugs directly. The PET radiotracer will be produced directly on the morning before the scanning by the Canadian Molecular Probe Consortium (“CanProbe”) in Toronto and transported to Buffalo. The contrast will be used during the PET scan

PROTOCOL TITLE: Open-label, single-blinded, observational, prospective, 36-month, longitudinal, controlled study to assess the efficacy of siponimod (Mayzent®) on microglia in patients with secondary progressive forms of multiple sclerosis

at the Center for Biomedical Imaging in accordance with EH&S *Radiation Safety* Program. The Ferumoxytol needed for research MRI scan will be kept in a locked cabinet in MRI suite available only to the investigators in the study.

Healthy controls will not be given a contrast agent during collection of the MRI scan.

**2.2** *If the drug is investigational (has an IND) or the device has an IDE or a claim of abbreviated IDE (non-significant risk device), include the following information:*

- *Identify the holder of the IND/IDE/Abbreviated IDE.*
- *Explain procedures followed to comply with sponsor requirements for FDA regulated research for the following:*

	Applicable to:		
FDA Regulation	IND Studies	IDE studies	Abbreviated IDE studies
21 CFR 11	X	X	
21 CFR 54	X	X	
21 CFR 210	X		
21 CFR 211	X		
21 CFR 312	X		
21 CFR 812		X	X
21 CFR 820		X	

Response: IND application is approved for 18F-PBR06. The IND approval by FDA is under the code “IND 156679”. The approval letter is included in the IRB submission.

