## 13.0 Provisions to Protect the Privacy Interests of Subjects

*13.1 Describe the steps that will be taken to protect subjects' privacy interests. "Privacy interest" refers to a person's desire to place limits on whom they interact or whom they provide personal information.*

Response: Potential participants will meet with a full-time study coordinator in a private room where no one can overhear. The potential participants are provided all information regarding the full testing battery, length of participation, and reimbursement and reminded that their participation is entirely voluntary. At this time, participants are also able to ask additional questions regarding their participation.

*13.2 Describe what steps you will take to make the subjects feel at ease with the research situation in terms of the questions being asked and the procedures being performed. "At ease" does not refer to physical discomfort, but the sense of intrusiveness a subject might experience in response to questions, examinations, and procedures.*

Response: MS patients are very familiar with the tests being performed as part of this study. They are able to ask questions at any time. They can decline to answer any questions if they find them intrusive or uncomfortable. MRI, PET and lab assessments are only performed by licensed personnel. Tests are conducted in private settings.

Healthy control subjects will only undergo 1 MRI and 1 PET scan.

*13.3 Indicate how the research team is permitted to access any sources of information about the subjects.*

Response: Specifically, data is accessible only by those who have been assigned to the study and have the requisite training and experience. Each study personnel have their own logon ids and passwords to access the secure network drive at BNAC. Dent and Great Lakes Medical Imaging will not be housing any study related data. After collection, all study materials are given to BNAC.

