**2023-09-15**

All statistical analyses were performed using SPSS version 28.0 (IBM, Armonk, NY, USA). The data distribution was determined using visual inspection of the histograms and Q-Q plots.

Categorical data was compared using chi-square test, parametric numerical data was compared using Student's t-test and non-parametric data using Mann Whitney U test. The comparisons between the groups were further adjusted for demographic and genetic differences using analysis of covariance (ANCOVA) and adjusted estimated means were shown as mean (standard error).

Due to the small sample size and non-parametric nature of the data, the correlations were performed using non-parametric Spearman's test. Pair-wise comparisons within the subjects were also performed. P-values lower than 0.05 were considered statistically significant. Due to the exploratory nature of the study, corrections for multiple comparisons were omitted. The data was additionally visualized using box and scatter plots.

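### The primary objective names no comparator and the SAP names no primary analysis, so a within-group change could be reported as a siponimod effect that the design cannot attribute to the drug

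*Combined protocol and SAP*

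**What the plan says.** **Objectives (Local Supplement, section 1.0).** The primary objective is "The assessment of the effect of Mayzent over at least 24 months on the evolution of microglia pathology"; the population is active SPMS. No comparator appears in it. Secondary objective (a) is to "compare the effect of Mayzent to the control group of active SPMS patients treated with ocrelizumab", measured by changes in microglial activation.

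**Selection (section 1.0).** A patient may qualify on imaging: "Activity is determined by MRI activity (contrast-enhancing lesions; new and unequivocally enlarging T2 lesions". Clinical activity also counts, alone or together with imaging, and the rule for it is "clinical relapses in the 24 months prior to the study baseline".

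**Assignment (section 2.1).** Treatment is not randomised: "The treatment provided to subjects is part of their routine clinical care as determined by their neurologist and the patients themselves".

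**Healthy controls (section 13.2).** "Healthy control subjects will only undergo 1 MRI and 1 PET scan".

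**Analysis (SAP, opening text dated 2023-09-15).** Group comparisons come first: chi-square, t or Mann-Whitney tests, then ANCOVA adjusting for demographic and genetic differences. Later, one sentence adds: "Pair-wise comparisons within the subjects were also performed". The threshold is p<0.05, and multiplicity correction is omitted because the study is exploratory. No test is tied to an objective and no primary endpoint is named. Baseline PET value and disease activity are not named as covariates.

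**Outcome (SAP, PET analysis).** Uptake is expressed as SUVR, referenced to the cerebellum.

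**The concern.** Read literally, the primary question is whether one treated group changes over time, and a within-subject test answers that question directly. Such a test compares the observed change with zero. Zero is the right reference only if nothing but the drug would move SUVR over 24 months.

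Three things could move it. Patients were chosen for activity before baseline, so PET measures may start off-centre and drift back. Imaging conditions may change; Revision History item 4 adds a second PET scanning site during the study. The untreated course of microglial activation is also unknown. Healthy controls seen once cannot show any of these.

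The study titles speak of assessing the efficacy of siponimod. If the siponimod group shows a significant fall, nothing in the SAP stops it being reported as efficacy. If the untreated course is upward, the same test could hide a real effect.

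**Working it through.** **Is there a figure in the plan to reproduce?** No. Section 1.0 gives 60 MS patients without effect size, SD, power or split by drug. Section 8.2 supports the number by feasibility only: about 10 prescriptions a month, 5 for each drug. I assume 30 siponimod patients and also show 15.

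**Model, with no drug effect.** Selection acts on activity before baseline and the outcome is SUVR, so any regression is indirect. Standardise both to unit variance and assume normality. All inputs below are assumptions.

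- p: share of SPMS patients meeting the activity rule (0.7 to 0.3).
- c: normal cut-off exceeded with probability p; i = φ(c)/p is the mean activity of those selected.
- g = ρ0 − ρ1: correlation of prior activity with PET at baseline, minus its correlation with PET at 24 months.
- r: correlation of baseline with 24-month PET (0.5 to 0.8).

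Formulas:

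- expected spurious fall = g × i
- variance of individual changes = 2(1 − r) − g² × i × (i − c)
- non-centrality = (fall ÷ SD of changes) × √n; rejection rate from the non-central t with n − 1 df, two-sided 0.05 (the SAP does not state sidedness).

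**Worked case.** p = 0.5, g = 0.2, r = 0.7, n = 30.

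- c = 0 and i = 0.3989/0.5 = 0.798
- fall = 0.2 × 0.798 = 0.16 SD
- variance = 0.6 − 0.04 × 0.637 = 0.5745; SD = 0.758
- non-centrality = (0.1596/0.758) × √30 = 1.15
- rejection rate = 20%, against a nominal 5%

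A simulation of 10,000 studies with ρ0 = 0.4 and ρ1 = 0.2 gave 20.2% for the paired test. Comparing the same change with 30 ocrelizumab patients selected in the same way gave 5.0%.

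**Range** over p = 0.7 to 0.3 and r = 0.5 to 0.8:

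| Gap g | Spurious fall (SD) | Paired test significant, n = 30 | n = 15 |
|---|---|---|---|
| 0 | 0 | 5% | 5% |
| 0.1 | 0.05 to 0.12 | 5.8% to 16.5% | 5.4% to 10.3% |
| 0.2 | 0.10 to 0.23 | 8.3% to 52.2% | 6.5% to 28.0% |

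The model covers regression to the mean only. Time trend and untreated course would add to it or offset it by amounts the documents do not allow one to estimate.

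**The case against.** The best reply is that the study is controlled. A concurrent ocrelizumab group meets the same activity definition, the SAP lists between-group tests first, and regression shared by both groups cancels in that comparison. The study is also called observational and exploratory. The form's instructions say the sponsor protocol is uploaded separately, so a primary analysis may be defined in a document not available here.

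Most of this stands, and it limits the point. It does not remove it: the controlled comparison is ranked second, and its ANCOVA omits baseline PET and activity although treatment was chosen by neurologist and patient. Calling the study exploratory explains the missing multiplicity correction but does not make a single-group change attributable to the drug.

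A reader might go further in three ways that the documents do not support.

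- *That the paired test is the primary analysis, or the only method for the primary objective.* The SAP ties no test to any objective.
- *That microglial activation declines naturally.* No section says so; it could rise.
- *That the usual formula for selection on the outcome gives the size.* With baseline k SD too high and test-retest correlation ρ, the expected fall is k(1 − ρ). For 30 pairs and ρ from 0.7 to 0.5, this gives 8% to 10% at k = 0.25, 18% to 26% at k = 0.5 and 54% to 75% at k = 1.0. The arithmetic is right, but it assumes selection on baseline SUVR. Here selection is on earlier lesions and relapses. If activity correlated 0.5 with PET, k = 1.0 would need i = 1/0.5 = 2, roughly the most active 6% of patients.

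**Conclusion.** The point holds as a gap in ranking and labelling. The primary objective has no comparator, no primary analysis is named, and an uncorrected within-subject test is available to fill the space. A siponimod-only change cannot be attributed to the drug, and the bias could run either way.

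The inflation may be nil. It is nil in this model if prior activity relates equally to PET at both times, and it shrinks with fewer patients. With moderate correlation gaps it can be several times the nominal 5%. These figures rest on an assumed arm of 30, a normal selection model and correlations that the documents do not give. They show that the risk is not negligible; they do not estimate it.

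The cancellation in the ocrelizumab comparison assumes that both groups were selected alike. Because that comparison is non-randomised and against an active drug, it supports a relative statement only.

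**What to change.** MS enrolment and follow-up are closed (Revision History, item 5), so the change is confined to analysis and reporting.

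1. State in the SAP that the within-group siponimod change is descriptive and carries no efficacy claim.
2. Base any efficacy statement on the between-arm difference in SUVR change from baseline.
3. Add baseline SUVR and baseline or prior activity (contrast-enhancing lesion, recent relapse) to the demographic and genetic ANCOVA covariates.
4. Word the conclusion as relative to ocrelizumab in a non-randomised comparison.

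**Cost.** SAP and report text, and a rerun of the ANCOVA. No new data should be needed: activity status was required for eligibility, and a baseline scan is needed for any change. An effect common to both drugs can no longer be claimed. The comparison is also less sensitive. With an assumed 30 per arm and 80% power (normal approximation), it detects (1.960 + 0.842) × √(2/30) = 0.72 SD of the individual changes, against (1.960 + 0.842)/√30 = 0.51 SD for the paired test. Baseline adjustment may recover some of this, at one degree of freedom for each added covariate.

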## 2.0 Study Intervention/Investigational Agent

2.1 *If the research involves drugs or device, describe your plans to store, handle, and administer those drugs or devices so that they will be used only on subjects and be used only by authorized investigators.*

- *If the control of the drugs or devices used in this protocol will be accomplished by following an established, approved organizational SOP (e.g., Research Pharmacy SOP for the Control of Investigational Drugs, etc.), please reference that SOP in this section.*

Response: The treatment provided to subjects is part of their routine clinical care as determined by their neurologist and the patients themselves. This project will not administer any drugs directly. The PET radiotracer will be produced directly on the morning before the scanning by the Canadian Molecular Probe Consortium (“CanProbe”) in Toronto and transported to Buffalo. The contrast will be used during the PET scan

PROTOCOL TITLE: Open-label, single-blinded, observational, prospective, 36-month, longitudinal, controlled study to assess the efficacy of siponimod (Mayzent®) on microglia in patients with secondary progressive forms of multiple sclerosis

at the Center for Biomedical Imaging in accordance with EH&S *Radiation Safety* Program. The Ferumoxytol needed for research MRI scan will be kept in a locked cabinet in MRI suite available only to the investigators in the study.

Healthy controls will not be given a contrast agent during collection of the MRI scan.

**2.2** *If the drug is investigational (has an IND) or the device has an IDE or a claim of abbreviated IDE (non-significant risk device), include the following information:*

- *Identify the holder of the IND/IDE/Abbreviated IDE.*
- *Explain procedures followed to comply with sponsor requirements for FDA regulated research for the following:*

	Applicable to:		
FDA Regulation	IND Studies	IDE studies	Abbreviated IDE studies
21 CFR 11	X	X	
21 CFR 54	X	X	
21 CFR 210	X		
21 CFR 211	X		
21 CFR 312	X		
21 CFR 812		X	X
21 CFR 820		X	

Response: IND application is approved for 18F-PBR06. The IND approval by FDA is under the code “IND 156679”. The approval letter is included in the IRB submission.

### **3.0 Inclusion and Exclusion Criteria\***

**3.1** *Describe any inclusion or exclusion criteria that will differ for your local site compared to the sponsor’s protocol. For example, if the sponsor’s protocol allows the enrollment of children but your site will not enroll children, indicate that here.*

Response: This is a 1 site study (BNAC). Inclusion/exclusion criteria will be standard across any MS subjects to be enrolled. 15-age-matched healthy controls (10 females and 5 males aged between 18-65 years) will be enrolled.

### **4.0 Withdrawal of Subjects\***

**4.1** *Describe procedures that will be followed locally, if different than the sponsor’s protocol, when subjects withdraw from the research.*

PROTOCOL TITLE: Open-label, single-blinded, observational, prospective, 36-month, longitudinal, controlled study to assess the efficacy of siponimod (Mayzent®) on microglia in patients with secondary progressive forms of multiple sclerosis

Response: Any premature withdrawal from the study will be recorded in the appropriate CRF. The person will be off study (no future assessments) and continue with standard of care as prescribed by his/her neurologist. If the subject discontinues the medication for medical reasons, every attempt will be made to complete the End of Treatment (EoT) testing schedule. The healthy control cohort is not being treated for any pathology related to a neurological disease.

## 5.0 Vulnerable Populations\*

5.1 *If the research involves individuals who are vulnerable to coercion or undue influence, describe additional safeguards included to protect their rights and welfare.*

- *If the research involves pregnant women, review “CHECKLIST: Pregnant Women (HRP-412)” to ensure that you have provided sufficient information.*
- *If the research involves neonates of uncertain viability or non-viable neonates, review “CHECKLIST: Neonates (HRP-413)” or “HRP-414 – CHECKLIST: Neonates of Uncertain Viability (HRP-414)” to ensure that you have provided sufficient information.*
- *If the research involves prisoners, review “CHECKLIST: Prisoners (HRP-415)” to ensure that you have provided sufficient information.*
- *If the research involves persons who have not attained the legal age for consent to treatments or procedures involved in the research (“children”), review the “CHECKLIST: Children (HRP-416)” to ensure that you have provided sufficient information.*
- *If the research involves cognitively impaired adults, review “CHECKLIST: Cognitively Impaired Adults (HRP-417)” to ensure that you have provided sufficient information.*
- *Consider if other specifically targeted populations such as students, employees of a specific firm or educationally/economically disadvantaged persons are vulnerable to coercion or undue influence. The checklists listed above for other populations should be used as a guide to ensure that you have provided sufficient information.*

Response: Not applicable

## 6.0 Sharing of Results with Subjects\*

6.1 *Describe whether or not results (study results or individual subject results, such as results of investigational diagnostic tests, genetic tests, or incidental findings) will be shared with subjects or others*

PROTOCOL TITLE: Open-label, single-blinded, observational, prospective, 36-month, longitudinal, controlled study to assess the efficacy of siponimod (Mayzent®) on microglia in patients with secondary progressive forms of multiple sclerosis  
(e.g., the subject's primary care physicians) and if so, describe how it will be shared.

Response: In the event that an incidental finding is discovered on the MRI images, the individual's neurologist or primary care physician will be notified.

## 7.0 Setting

### 7.1 *Describe the local sites or locations where your research team will conduct the research.*

Response: For all participants, the MRI will take place at Buffalo General Hospital. The PET exam will take place at the CBI, located on the CTRC, 7th Floor or at Great Lakes Medical Imaging (GLMi) (**[name]**).

For BNAC participants, clinical visits will take place at UBMD Neurology, located in the Conventus building at [name] on the 4th floor.

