### **Revision History**

Revision #	Version Date	Summary of Changes	Consent Change?
1	24/06/2021	Change based on the new study protocol	Yes
2	28/02/22	Addition of Dent Institute as a recruitment and testing site	New MS consent for DENT; Yes to current MS consent form

PROTOCOL TITLE: Open-label, single-blinded, observational, prospective, 36-month, longitudinal, controlled study to assess the efficacy of siponimod (Mayzent®) on microglia in patients with secondary progressive forms of multiple sclerosis

3	07/04/2022	Inclusion of 15 healthy controls to undergo 1 PET scan and 1 MRI scan.	New HC consent form
4	11/9/2022	Including Great Lakes Medical Imaging as a PET scanning site	No
5	03/03/2023	Closing enrollment and follow-up of MS patients; Closure letter; continued enrollment of HCs	Yes - HC

PROTOCOL TITLE: Open-label, single-blinded, observational, prospective, 36-month, longitudinal, controlled study to assess the efficacy of siponimod (Mayzent®) on microglia in patients with secondary progressive forms of multiple sclerosis

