### 7.3 *Identify where research procedures will be performed.*

Response:

For all participants, the MRI will take place at Buffalo General Hospital. The PET exam will take place at the CBI, located on the CTRC, 7th Floor or at Great Lakes Medical Imaging (GLMi).

For BNAC participants, clinical visits will take place at UBMD Neurology, located in the Conventus building at [name] on the 4th floor. For MS subjects, the clinical visit, demographic and MRI screen questionnaires will be administered at Buffalo General Hospital.

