## 11.0 Local Number of Subjects

*11.1 Indicate the total number of subjects to be accrued locally.*

Response: 60 MS (no longer applicable); 15 HCs

*11.2 If applicable, distinguish between the number of subjects who are expected to be enrolled and screened, and the number of subjects*

PROTOCOL TITLE: Open-label, single-blinded, observational, prospective, 36-month, longitudinal, controlled study to assess the efficacy of siponimod (Mayzent®) on microglia in patients with secondary progressive forms of multiple sclerosis  
*needed to complete the research procedures (i.e., numbers of subjects excluding screen failures.)*

- Response: We estimate that 90 MS patients will need to be screened in order to achieve our enrollment goal of 60. *No longer applicable*
- Healthy control subjects will be from other studies which they participated in and consented to be contacted for participation in future studies.

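### PET may be done at two sites, but the SAP has no scanner term and no same-scanner condition; if both scanners were used, a residual regional offset could bias patient-versus-control comparisons and within-patient change

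*Combined protocol and SAP*

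**What the plan says.** **Where PET is done.** Sections 7.1 and 7.3 of the local supplement give one location, "The PET exam will take place at the CBI, located on the CTRC", and then an alternative, "Floor or at Great Lakes Medical Imaging (GLMi". Neither section says who goes where. In the same answers, MRI is fixed at one hospital for everyone. Section 2.1 places the PET scan only "at the Center for Biomedical Imaging in accordance with" the radiation safety programme.

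**When.** The Revision History has three relevant entries:
- Revision 3 (07/04/2022): "Inclusion of 15 healthy controls to undergo 1 PET scan and 1 MRI scan".
- Revision 4 (11/9/2022): "Including Great Lakes Medical Imaging as a PET scanning site".
- Revision 5 (03/03/2023): "Closing enrollment and follow-up of MS patients; Closure letter; continued enrollment of HCs".

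**What PET is for.** In the Study Summary (Section 1.0) the primary objective is how microglial pathology evolves under siponimod over 24 months or more. The secondary objectives compare siponimod with ocrelizumab. They also give the healthy controls a role: "to use as a statistical control group (15 HCs) when looking at an increase in TSPO in a parametric map of the brain". Section 11.1 gives the numbers as "60 MS (no longer applicable); 15 HCs".

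**How it is analysed.** The SAP, dated 2023-09-15, postdates all of these revisions. It adjusts comparisons between unnamed groups by ANCOVA for demographic and genetic factors, and adds pair-wise comparisons within subjects. Its PET analysis section describes motion alignment, SUV, a ratio to the cerebellum (to handle individual tracer kinetics) and partial-volume correction in PETPVC. It does not mention scanner, site, cross-calibration or a point-spread width.

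**The concern.** Two PET scanners can differ in scatter handling, reconstruction and resolution. Whatever regional difference survives the processing enters SUVR as an offset tied to the scanner. Two uses of the PET data are open to it.

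- **MS patients against healthy controls.** The second site became available shortly before MS follow-up closed, and it stayed available to controls afterwards. Unequal site shares are therefore plausible, and an offset would be read as a TSPO difference.
- **Within-patient change.** This bears on the primary objective. If a patient's earlier scan was at CBI and the later one at the second site, the offset is read as change under treatment.

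Siponimod against ocrelizumab is exposed only if the two arms used the sites unequally, because an additive offset cancels when shares are equal.

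**Working it through.** The plan gives no PET standard deviation, effect size or power, so there is no figure to reproduce. The dates, visit structure and 15 controls come from the documents. The offset, site shares, switching shares and number of MS patients are assumptions. Tests are taken as two-sided at 0.05.

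**1. How long MS patients could use the second site.** The date 11/9/2022 can be read two ways. The log's unambiguous dates (24/06/2021, 28/02/22) are day-first, but this entry is not zero-padded like its neighbours.
- 11 September 2022 to 3 March 2023: 173 days.
- 9 November 2022 to 3 March 2023: 114 days.

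Controls were added earlier (157 days earlier, reading both dates day-first), so both groups may overlap at CBI.

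**2. What that window means for pairs.** Section 10.5 pays 50 + 100 (PET) + 100 (MRI) = 250 dollars per time point, and 5 x 250 = 1,250 dollars in all, which implies PET at each of five visits. The lesion section of the SAP implies visit intervals of 6, 6, 12 and 12 months. A window of 114 to 173 days is shorter than 6 months (about 182 days). It therefore holds at most about one scheduled visit per patient. If visits were on schedule and the revision dates bound actual use, the scan before a follow-up at the second site would have been at CBI. That follow-up could also be the patient's last, because the window ends when MS follow-up closes. The share of pairs that cross scanners is thus unknown, from 0 to nearly all.

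**3. What the cerebellar ratio removes.** A common gain cancels: 1.10/1.10 = 1.00. A regional one does not: 1.05 in the target and 1.00 in the cerebellum leave 1.05.

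**4. MS against controls, no true difference.** Shift = share gap x offset, in within-group SDs. Noncentrality = gap x offset / sqrt(1/15 + 1/n), with 15 + n - 2 degrees of freedom. For n = 20, the square root is 0.342; a gap of 0.5 and an offset of 0.5 give 0.25/0.342 = 0.73, hence 11%.

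| MS patients | Offset (SD) | Gap 0.25 | Gap 0.5 | Gap 1 |
|---|---|---|---|---|
| 20 | 0.3 | 5.5% | 7% | 14% |
| 20 | 0.5 | 6.5% | 11% | 30% |
| 20 | 0.8 | 9% | 21% | 62% |
| 10 | 0.5 | 6% | 9% | 22% |

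With no gap the rate is 5%. A simulation with 9/15 controls and 2/20 patients at the second site (offset 0.5 SD) gave 10.4% unadjusted, 5.0% with a scanner covariate, and 5.0% restricted to the first scanner. With 15/15 against 0/20, scanner and group coincide and the covariate model cannot be fitted.

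**5. Within-patient change, no true change.** Offset 0.5 SD of change. Noncentrality = switching share x 0.5 x sqrt(n), with n - 1 degrees of freedom. For n = 20 and 50% switching: 0.5 x 0.5 x 4.47 = 1.12, hence 19%.

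| n | 10% switch | 25% | 50% | 95% |
|---|---|---|---|---|
| 10 | 5% | 6.5% | 11% | 27% |
| 20 | 5.5% | 8% | 19% | 52% |
| 30 | 6% | 10% | 26% | 71% |

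Both formulas treat the offset as a pure mean shift. Simulating explicit switchers gives slightly lower rates (7.5% rather than 8% for 5 of 20).

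**The case against.** The strongest reply is that every consequential step is unseen. No text shows that the second site scanned anyone, that its scanner differs from the first, how many scans each site did, or that any regional offset exists. Revision dates are not scan dates. The supplement's instructions say that the sponsor protocol is uploaded separately, and it may hold a scanner rule. All of this stands, and it limits confidence.

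Second, the SAP never mentions healthy controls. Their role comes from a secondary item in the Study Summary, which speaks of a parametric map and not of a regional ANCOVA. This also stands: it would be wrong to say that the SAP's ANCOVA for MS against controls is biased, because the SAP specifies no such model.

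Third, the processing already helps. It does in part. The ratio removes a common gain, and partial-volume correction reduces resolution differences. Neither is shown to remove regional differences from scatter, reconstruction or an unmatched point-spread width.

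Fourth, the SAP calls the study exploratory and makes no multiplicity correction, so nominal error rates carry limited weight. That lowers the priority, but a biased estimate is no less biased in an exploratory study.

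A reader might also infer that the short window makes within-patient change safe. The documents do not support that: the window ends at closure of follow-up, so scans in it may be the last of their pairs.

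**Conclusion.** The concern holds as a conditional gap. Two PET sites are allowed without an assignment rule, and the SAP neither adjusts for scanner nor requires same-scanner pairs. If both scanners were used and a regional offset remains, MS-versus-control comparisons are biased by the share gap times the offset, and mean within-patient change by the switching share times the offset. The illustrated false-positive rates run from close to the nominal 5% to well above it, and rest wholly on assumed offsets, shares and patient numbers. The actual size is unknown and may be zero.

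A reader might go further and conclude that the PET results are confounded by scanner, or that all controls were scanned on one machine and all patients on another. The documents do not show this. Early overlap at CBI was possible, which makes complete separation less likely.

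This is a cheap improvement, with low to medium confidence.

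**What to change.** 1. Tabulate PET scans by scanner, group and visit. If only one scanner was used, say so; steps 2 to 4 then fall away.
2. If both were used, report each PET group comparison, and any MS-versus-control map, with scanner as a covariate beside the planned result, provided that both groups overlap on both scanners. At least 3 scans per group on each scanner is one workable rule, and is a judgement. Where overlap is poorer, restrict to one scanner or state that group and scanner cannot be separated.
3. Repeat the within-subject comparisons in same-scanner pairs.
4. State the point-spread width used in PETPVC, and use each scanner's own.
5. Reconcile Section 2.1 with Sections 7.1 and 7.3 on where PET is done.

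**Cost.** No extra scans are needed: a table, one degree of freedom, and a re-run of partial-volume correction if one common width was applied to both scanners. The covariate multiplies the group standard error by 1/sqrt(1 - r^2), where r is the group-scanner correlation. For 15 controls and 20 patients:
- 6/15 against 3/20 at the second site: r = 0.283, 1.04-fold.
- 12/15 against 3/20, the worst case under the 3-scan rule: r = 0.65, 1.32-fold.
- 14/15 against 1/20: r = 0.883, 2.1-fold, so the covariate is not advised.
- 9/15 against 2/20 falls below the 3-scan rule. Restricting it to the first scanner leaves 6 against 18: sqrt(1/6 + 1/18) / sqrt(1/15 + 1/20) = 0.471/0.342 = 1.38-fold.

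The pair analysis loses every switcher: 2 of 20 at 10%, 10 of 20 at 50%. If nearly all patients switched, few pairs would remain, and the report should say that change cannot be separated from scanner.
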